6.3 Dose Modifications/Delays

No ofatumumab dose modifications are permitted.

CONFIDENTIAL

This document is confidential. Do not disclose or use except as authorized.

7. DRUG FORMULATION AND ADMINISTRATION

Table 6. Recommendations for Dose Modification of Study Drug(s) Based on Type and Severity of Adverse Event or Laboratory Abnormality

Non-Hepatic and Non-Hematological Study Drug-Related Event				
CTCAE Grade	Grade 1	Grade 2	Grade 3	Grade 4
Idelalisib and Ofa Dosing Recommendation	Maintain dose level	Maintain dose level	Withhold drugs until toxicity is Grade ≤1. May resume idelalisib only at next lower dose level for most toxicities, but may resume at current dose level in the case of grade 3 infections, grade 3 nausea/vomiting/diarrhea that can be symptomatically managed, grade 3 asymptomatic laboratory abnormalities or grade 3 infusion reactions.	
Hepatic Study Drug-Related Event (Elevation in ALT, AST, or Bilirubin)				
CTCAE Grade	Grade 1	Grade 2	Grade 3	Grade 4
ALT/AST	>ULN-3 x ULN	>3-5 x ULN	>5-20 ULN	>20 x ULN
Bilirubin	>ULN-1.5 x ULN	>1.5-3 x ULN	>3-10 x ULN	>10 x ULN
Idelalisib and Ofa Dosing Recommendation	See Section 6.2: Management of Hepatic Events.			
Hematological Idelalisib -Related Event				
IWCLL Grade	Grade 1	Grade 2	Grade 3	Grade 4
Neutropenia (ANC x 10 ⁹ /μL)	ANC <LLN-1.5	ANC <1.5-1.0	ANC <1.0-0.5	ANC <0.5
Thrombocytopenia (platelets x 10 ⁹ /μL)	Platelets 11-24% below baseline	Platelets 25-49% below baseline	Platelets 50-74% below baseline	Platelets ≥75% below baseline or ≤25K
Idelalisib Dosing Recommendation	Maintain dose level	Maintain dose level	Maintain dose level; support with g-CSF growth factors at investigator discretion	During combination therapy period, consider G-CSF support and maintain current study drug dose level and schedule. During initial and continuing single-agent study drug therapy period, consider G-CSF support and continue study drug at initial or lower dose level at investigator discretion.

***Note: In any case where Idelalisib is held, ofatumumab should also be held. The assessment schedule is also held in cases where study drug is held for greater than half a week.*

Abbreviations: ALP, alkalkine phosphatase; ALT, alanine aminotransferase; ANC, absolute neutrophil count; AST, aspartate aminotransferase; CTCAE, Common Terminology Criteria for Adverse Events; LLN, lower limit of normal; ULN, upper limit of normal

7.1 Idelalisib

7.1.1 Drug Substance and Formulation

Idelalisib is a fluorinated quinazolinone with 1 stereogenic center. Idelalisib is the *S* enantiomer. The compound has no known structural similarity to existing drugs. The drug substance is a white to off-white, crystalline powder with a chemical formula of C₂₂H₁₈FN₇O, a molecular weight of ~415 Daltons, and low aqueous solubility. Idelalisib is orally bioavailable.

CONFIDENTIAL

This document is confidential. Do not disclose or use except as authorized.

7.1.2 Description

Idelalisib is manufactured according to cGMP. The study drug is provided in tablets intended for oral administration. Each tablet contains 100, or 150 mg of the active study drug substance. Inactive excipients present in the formulation are microcrystalline cellulose, hydroxypropyl cellulose, croscarmellose sodium, sodium starch glycolate, and magnesium stearate. The 100-mg tablets are orange, and the 150-mg tablets are pink. The yellow coating contains yellow iron oxide, polyethylene glycol, talc, polyvinyl alcohol polymer, and titanium dioxide. The orange coating contains Food Drug & Cosmetic Yellow #6/Sunset Yellow Food Cosmetic Formulary Aluminum Lake, polyethylene glycol, talc, polyvinyl alcohol polymer, and titanium dioxide. The pink coating contains red iron oxide, polyethylene glycol, talc, polyvinyl alcohol polymer, and titanium oxide.

7.1.3 Packaging

Idelalisib will be packaged in bottles containing 60 tablets. A label will be affixed to each bottle and will contain the following information in English:

- Manufacturer name and address
- Protocol identifier
- Description of contents, including dose strength and fill count
- Caution statement (includes “keep out of reach of children” statement)
- Storage conditions
- Manufacture date
- Lot number

7.1.4 Source

Idelalisib will be supplied free of charge by Gilead Sciences. Biologics has been selected for the provision of supply procurement and distribution services to each investigative site. Any questions or concerns regarding study drug supply should be referred to DFCI team and Biologics for routing to Gilead Sciences clinical project manager.

7.1.5 Storage and Stability

Bottles containing tablets of idelalisib will be stored at controlled room temperature (~15 to 30°C). While stability of tablets stored at controlled room temperature has been confirmed, brief excursions to temperatures up to 40°C or down to 5°C will not adversely affect the drug. Freezing must be avoided. Stability data at the start of study will support the use of the drug product for ≥ 12 months. The clinical site will be updated as more stability data become available.

7.1.6 Dispensing

The clinic pharmacist or an alternative qualified person will be responsible for dispensing study medication. It is planned that drug will be dispensed at 4-week intervals through the first 24 weeks of treatment and at 12-week intervals thereafter. A modest overage will be supplied such that patients have sufficient drug in case of loss, spillage, or necessary deviations in scheduling clinic returns (eg, due to inclement weather, holidays, etc). Tablets should be kept in the original bottles provided. However, it is permissible to re-package the quantity of study

CONFIDENTIAL

This document is confidential. Do not disclose or use except as authorized.

medication into standard amber prescription bottles in the case the need arises (e.g. participant requires a lesser quantity of medication due to dose reductions).

7.1.7 Return

Patients should return all unused study medication to the study site at each applicable study visit.

7.1.8 Accountability

The disposition of all idelalisib study drug should be documented from the time of receipt at the site through patient dispensing and return.

Study personnel must ensure that all study drug is kept in a secure locked area with access limited to authorized personnel. The study drug must not be used outside the context of this protocol. Under no circumstances should the investigator or site personnel supply study drug to other investigators or clinics, or allow the study drug to be used other than as directed by this protocol.

The investigator and/or the responsible site personnel must maintain accurate records of the receipt of all study drug shipped by Gilead Pharmaceuticals or its designee, including, but not limited to, the date received, lot number, amount received, and the disposition of all study drug. Study drug accountability records must also be maintained that include the patient number to whom the study drug was dispensed and the date, quantity and lot number of the study drug dispensed.

The study drug supply should be retrieved from patients at the end of each dosing interval. The quantity of study drug and the date returned by the patient should be recorded in the study drug accountability records.

Remaining unused study drug supply will be destroyed at the clinical site, standard institutional policy should be followed. Records documenting the date of study drug destruction, relevant lot numbers, and destroyed should be maintained.

7.1.9 Overdose Precautions

For this protocol, an overdose is defined as administration of >700 mg of idelalisib in a single day. In a patient who experiences an overdose of this magnitude, idelalisib administration should be temporarily interrupted. If the overdose ingestion is recent and substantial, and if there are no medical contraindications, use of gastric lavage or induction of emesis may be considered. Observation for any symptomatic side effects should be instituted, and vital signs and biochemical and hematological parameters should be followed closely (consistent with the protocol or more frequently, as needed). Appropriate supportive management to mitigate adverse effects should be initiated.

The Gilead Sciences medical expert should be contacted if an overdose occurs. Under applicable regulations, overdosing may result in a serious adverse event and may require reporting accordingly (see Section 11 below).

7.1.10 Inadvertent Exposure and Spill Precautions

Based on available data from nonclinical studies, idelalisib does not appear to be acutely toxic, genotoxic, or irritative at levels that are likely to result from inadvertent exposure to the contents

CONFIDENTIAL

This document is confidential. Do not disclose or use except as authorized.

of broken capsules or tablets. Personnel handling the drug should use reasonable precautions to avoid eye contact, skin contact, inhalation, or ingestion of the study drug product. For further information regarding inadvertent exposure and spill precautions, please consult the idelalisib investigator brochure.

7.2 Ofatumumab

7.2.1 Medication

GlaxoSmithKline will supply commercial ofatumumab free of charge. Biologics has been selected for the provision of supply procurement and distribution services to each investigative site as content-labeled Ofatumumab vials presented as either 100 mg – acetate formulation, 20 mg/mL, 5 mL fill vials; or 1000 mg – acetate formulation, 20 mg/mL, 50 mL fill vials.

The medical product, ofatumumab, is a liquid concentrate for solution for infusion presented in glass vials. Ofatumumab will be infused intravenously as specified above in Section 5.2.2.

The ofatumumab infusions will be prepared in 1000 mL NaCl sterile, pyrogen free 0.9% NaCl to yield a 0.3 mg/mL or 1 mg/mL ofatumumab concentration for infusions of 300 mg or 1000 mg, respectively.

Ofatumumab vials must be stored at 2-8°C. Protect from light and do not freeze. No special packaging components, other than the outer white cardboard carton in which the vials are placed, will be used to afford light protection.

Ofatumumab open-labeled product will be for intravenous infusion. The site is responsible for labeling individual vials for investigational use.

All items required for administration of study medication (e.g., infusion bags, etc.) are to be provided by the site. Filters will be supplied with commercial drug.

7.2.2 Composition of Ofatumumab Injection 20 mg/mL

The quantitative composition of acetate formulation 20 mg/mL. This is available in two fill volumes, 5 mL / vial (100 mg/vial) and 50 mL/vial (1000 mg/vial).

Ingredient	Quantity/ mL
Ofatumumab	20.0 mg
Sodium Acetate, Trihydrate	6.80 mg
Edetate Disodium, Dihydrate (EDTA)	0.019 mg
Polysorbate 80	0.20 mg
L-Arginine	10.0 mg
Sodium Chloride	2.98 mg

CONFIDENTIAL

This document is confidential. Do not disclose or use except as authorized.

Hydrochloric Acid	to give pH 5.5
Water for Injection	q.s. to 1.0 mL

7.2.3 Preparation of Ofatumumab Infusion

Ofatumumab will be prepared as 1000 mL dilution of ofatumumab in sterile, pyrogen-free 0.9% NaCl. The expiration time which is calculated based on the exact dilution time into the 0.9% NaCl must be written on the label of the infusion bag.

Once diluted into saline, the product is stable for up to 24 hours at ambient temperature. However, the product contains no preservative and should be used as soon as possible after dilution.

Preparation of drug solution for intravenous injection by the site pharmacist or designee will be done in accordance with the protocol, and in these dilution instructions. Ofatumumab intravenous solution will be prepared using standard dilution methods and following general aseptic practice standard to preparation of IV medications. Eyes and hands should be protected when handling ofatumumab.

For intravenous administration, compatibility of the following components for ofatumumab in clinical studies (i.e., not for commercial product) has been established:

Table 7: Dosing Components for Ofatumumab in Clinical Studies

Dosing component	Material of construction	Suggested Vendor
1L Saline Bags	Polyvinyl Chloride (PVC)	Baxter
	Polyolefin [polyethylene* (PE)/polypropylene (PP)]	Baxter, B. Braun
Administration Set	PVC	Baxter
	PVC lined with Polyethylene	B. Braun

Preparation of the 1000 mL infusion bags should be done on the day of planned infusion.

* polyethylene (IUPAC name: polyethene)

7.2.3.1 Materials for Preparation and Administration of Infusion

The following materials are needed when preparing and administering the infusion:

CONFIDENTIAL

This document is confidential. Do not disclose or use except as authorized.

- 1000 mL sterile pyrogen free 0.9% saline (NaCl) infusion bag(s). The solution can be kept at ambient temperature for a maximum of 24 hours after preparation; however, the product does not contain a preservative and dosing should begin as soon as possible after dose preparation.
- Ofatumumab 100 mg and 1000 mg vials (supplied by Novartis)
- Needles and syringes (50 mL sterile syringe) not supplied by Novartis
- Intravenous (IV) cannula (not required if subject has central venous access) [not supplied by Novartis]
- Infusion pump (not supplied by Novartis) and infusion tubing set (supplied by Novartis)

7.2.3.2 Dilution of Ofatumumab

- Ensure the correct container number is used.
- Take a 1000 mL infusion bag (sterile pyrogen free 0.9% saline), remove and dispose of the appropriate amount of saline according to Table 8 or Table 9 below
- Draw the required amount of ofatumumab according to Table 2 (100 mg vials) or Table 3 (1000 mg vials) below
- Inject ofatumumab into the saline bag
- Invert the infusion bag slowly 3 times, avoiding formation of any foam
- Label the infusion bag with the completed label

Table 8: Preparation of Ofatumumab Infusion: 100 mg vials

Dose of Ofatumumab	Infusion bag size	Volume of NaCl to be removed from infusion bag	Volume of ofatumumab (number of ofatumumab vials)
300 mg	1000 mL	15 mL	15 mL (3 vials, 5 mL/vial)
1000 mg	1000 mL	50 mL	50 mL (10 vials, 5 mL/vial)

Table 9: Preparation of Ofatumumab Infusion: 1000 mg vials

Dose of Ofatumumab	Infusion bag size	Volume of NaCl to be removed from infusion bag	Volume of ofatumumab (number of ofatumumab vials)
1000 mg	1000 mL	50 mL	50 mL (1 vial, 50 mL/vial)

CONFIDENTIAL

This document is confidential. Do not disclose or use except as authorized.

7.2.4 Ofatumumab Infusion Set up

Ofatumumab must be administered by IV infusion through an in-line filter and through a well-functioning IV catheter (IV cannula) into a vein in the arm (or other venous access) by an infusion pump.

Please Note: It is mandatory to use an in-line low protein binding 0.2 micron polyether sulfone filter for all IV dosing of ofatumumab drug product.

DO NOT ADMINISTER AS AN INTRAVENOUS PUSH OR BOLUS.

Ofatumumab should not be mixed with any other medication. The intravenous line should be flushed with normal saline before and after completion of each infusion.

Please note that the infusion site can be used for blood sampling only if there is no risk of contamination of the infusion needle with the saline, infusion solutions, or any other fluid(s). Only a newly inserted needle can be used for the predose blood samples.

[figure not shown]
- Check subject ID against the label on the infusion bag and ensure the expiry of the solution. The solution must be administered in its entirety to the subject within 24 hours from time of preparation.
- Attach the 1000mL infusion bag to the infusion set (if not done at the pharmacy).
- Attach the in-line filter to the infusion set (closest to the subject; see Figure 1). **Note: The in-line filter must be used during the entire infusion.**
- Prime the infusion set and filter with ofatumumab (if not done at the pharmacy).
- In case of a problem with the filter (i.e. clogging/blockage), please change, re-prime the new filter, and continue the infusion.
- In case of problem with infusion set, follow local procedures.
- Collect the pre-dose blood samples, if required.
- Check the backflow from the IV cannula according to routine practice at site
- Set the pump at the initial infusion rate 12mL/hr for the first infusion and 25mL/hr for the subsequent infusions (if no grade ≥ 3 infusion-associated AEs were observed in the previous infusion)
- Start the infusion using the infusion rates and directions above in section 5.2.2.

No ofatumumab dose modifications are permitted.

CONFIDENTIAL

This document is confidential. Do not disclose or use except as authorized.

Figure 1: Infusion Set-Up Schematic

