5. TREATMENT PLAN

Treatment will be administered on an outpatient basis. Expected toxicities and potential risks as well as dose modifications for ofatumumab are described in Section 6 (Expected Toxicities and Dosing Delays/Dose Modification). No investigational or commercial agents or therapies other than those described below may be administered with the intent to treat the participant's malignancy.

Idelalisib lead-in followed by ofatumumab 8 wks later

All therapy with idelalisib has been discontinued. Patients on drug stopped as of 3/11/16. Those currently receiving ofatumumab may complete the planned course and evaluations as below. Those who have not yet reached day 57 may initiate ofatumumab at present. On day 57, ofatumumab will begin with the 300 mg dose. Ofatumumab will then be administered at 1000 mg weekly to complete 8 weeks (days 64, 71, 78, 85, 92, 99, 106) throughout Cycles 3 and 4. Cycle 4 will last 49 days (7 weeks) to accommodate the Ofatumumab dosing schedule. This will be followed by monthly ofatumumab on weeks 20, 24, 28, 32 to complete 4 additional cycles (5-8). The overall induction treatment period will then be up to 8 months, including whatever idelalisib was received prior to March 11, 2016. Restaging with CT scans will happen after Cycle 2, on cycle 4 day 22, and a final restage will occur 2 months after the completion of ofatumumab. There will be a tumor response assessment done via physical exam after Cycle 8.

Table 1: Treatment Description

Agent	Pre-medications; Precautions	Dose	Route	Schedule	Cycle Length
Idelalisib	None	150 mg BID	Oral	Discontinued	28 days (4 weeks) (Except cycle 4-49 days, 7 weeks)
Ofatumumab	Pre-medication before each ofatumumab infusion must be given within 30 minutes to 2 hours prior to the treatment: Acetaminophen 1000 mg po Benadryl 50 mg IV or po Methylprednisolone 50 mg IV*	300 mg at 0.3 mg/ml in NS; followed one week later by 1000 mg at 1 mg/ml in NS	IV after administration of Idelalisib and premeds	Weekly x 8 doses, then monthly x 4 doses	
* If the 2 nd infusion has been completed without the subject experiencing any grade = 3 AEs, pre-medication with glucocorticoid may be reduced or omitted before the 3 rd to N th infusion at the discretion of the investigator.					

CONFIDENTIAL

This document is confidential. Do not disclose or use except as authorized.

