5.2 Agent Administration

5.2.1 Idelalisib will not be given

5.2.2 Ofatumumab

The dosing of ofatumumab in CLL should consist of an infusion of 300 mg on Day 1, an infusion of 1000 mg weekly for 7 additional doses, and then infusions of 1000 mg monthly for up to 4 doses. The monthly ofatumumab doses should be given on Day 1 of the cycles.

First Infusion of 300 mg Ofatumumab (CLL)

The first dose administered of ofatumumab in CLL should be 300 mg to minimize infusion reactions. The initial rate of the first infusion of 300 mg ofatumumab (0.3 mg/mL) should be 12 mL/h. If no infusion reactions occur the infusion rate should be increased every 30 minutes, to a maximum of 400 mL/h, according to Table 2. If this schedule is followed, the infusion duration will be approximately 4.6 hours. If the ofatumumab dose cannot be completed on day 1 in clinic, the remaining dose may be completed the following day with the same premedications.

Table 2: Infusion rate at 1st ofatumumab infusion (300 mg)

Time	mL/hour
0 – 30 minutes	12
31 – 60 minutes	25
61 – 90 minutes	50
91 – 120 minutes	100
121 - 150 minutes	200
151 - 180 minutes	300
181+ minutes	400

CONFIDENTIAL

This document is confidential. Do not disclose or use except as authorized.

If an infusion reaction develops, the infusion should be temporarily slowed or interrupted. Upon restart, the infusion rate should be half of the infusion rate at the time the infusion was paused. If, however, the infusion rate was 12 mL/hour before the pause, the infusion should be restarted at 12 mL/hour. Thereafter, the infusion rate may be increased according to the judgment of the investigator, in the manner described in this section. If the infusion is not completed on day 1, the remaining infusion may be completed on day 2 at the starting infusion rate used on day 1.

First Infusion of 1000 mg Ofatumumab

The initial rate of the first infusion of 1000 mg ofatumumab (1 mg/mL) should be 12 mL/h. If no infusion reactions occur the infusion rate should be increased every 30 minutes, to a maximum of 400 mL/h, according to Table 3. If this schedule is followed, the infusion duration will be approximately 4.6 hours. If the ofatumumab dose cannot be completed on day 1 in clinic, the remaining dose may be completed the following day with the same premedications.

Table 3: Infusion rate at 1st ofatumumab infusion (1000 mg)

Time	mL/hour
0 – 30 minutes	12
31 – 60 minutes	25
61 – 90 minutes	50
91 – 120 minutes	100
121 - 150 minutes	200

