151 - 180 minutes	300
181+ minutes	400

If an infusion reaction develops, the infusion should be temporarily slowed or interrupted. Upon restart, the infusion rate should be half of the infusion rate at the time the infusion was paused. If, however, the infusion rate was 12 mL/hour before the pause, the infusion should be restarted at 12 mL/hour. Thereafter, the infusion rate may be increased according to the judgment of the investigator, in the manner described in this section. If the infusion is not completed on day 1, the remaining infusion may be completed on day 2 at the starting infusion rate used on day 1.

Subsequent Infusions of 1000 mg Ofatumumab

If the previous infusion has been completed without grade ≥ 3 infusion-associated AEs, the subsequent infusion of the 1000 mg ofatumumab (1 mg/mL) can start at a rate of 25 mL/hour and should be doubled every 30 minutes up to a maximum of 400 mL/h, according to Table 4. Duration of the infusion will be approximately 4 hours if this schedule is followed. If the previous infusion has been completed with grade ≥ 3 infusion-associated AEs, the subsequent infusion should start at a rate of 12 mL/hour according to Table 3 for CLL.

Table 4: Infusion rate at subsequent ofatumumab infusion

Time	mL/hour
0 – 30 minutes	25
31 – 60 minutes	50

CONFIDENTIAL

This document is confidential. Do not disclose or use except as authorized.

61 – 90 minutes	100
91 – 120 minutes	200
121+ minutes	400

During infusion the participant should be monitored closely and appropriate measurements should be performed whenever judged necessary. If the ofatumumab dose cannot be completed on day 1 in clinic, the remaining dose may be completed the following day with the same premedications. If the infusion is not completed on day 1, the remaining infusion may be completed on day 2 at the starting infusion rate used on day 1.

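### Sections 7.2.4 and 5.2.2, read literally, give different starting pump rates (25 versus 12 mL/h) for the second ofatumumab infusion when the first caused no grade 3 or higher infusion reaction

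*Combined protocol and SAP*

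**What the plan says.** Section 5.2.2 sets the dose sequence as "an infusion of 300 mg on Day 1, an infusion of 1000 mg weekly for 7 additional doses", followed by monthly doses. Infusion 2 is therefore the first at 1000 mg. The section then defines three classes of infusion:

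- The 300 mg infusion, Table 2: "The initial rate of the first infusion of 300 mg ofatumumab (0.3 mg/mL) should be 12 mL/h".
- The first 1000 mg infusion, Table 3: "The initial rate of the first infusion of 1000 mg ofatumumab (1 mg/mL) should be 12 mL/h". No exception is made for a patient who tolerated the 300 mg dose.
- Later 1000 mg infusions, Table 4: if the previous infusion caused no grade 3 or higher infusion-associated event, "the subsequent infusion of the 1000 mg ofatumumab (1 mg/mL) can start at a rate of 25 mL/hour".

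The set-up checklist in section 7.2.4 has two classes: "Set the pump at the initial infusion rate 12mL/hr for the first infusion and 25mL/hr for the subsequent infusions". A parenthesis after these words puts the same adverse-event condition on the 25 mL/h setting. The next bullet tells staff to start the infusion using the rates in section 5.2.2.

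Section 5 stops idelalisib but lets ofatumumab continue, including for new starters: "Those who have not yet reached day 57 may initiate ofatumumab at present".

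**The concern.** The 7.2.4 bullet does not mention dose strength. Counted in order of administration, infusion 1 is the first and infusion 2 is already a subsequent one. If infusion 1 passed without a grade 3 or higher infusion-associated event, the checklist sets the pump at 25 mL/h for an infusion that 5.2.2 starts at 12 mL/h. If infusion 1 did cause such an event, the sections do not conflict, because the 25 mL/h condition in 7.2.4 is not met.

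Section 6.1.2 names infusion reactions as the primary adverse event of ofatumumab, and infusion 2 is the first at 1 mg/mL rather than 0.3 mg/mL. The protocol also treats infusion 2 as distinct elsewhere: the footnote to Table 1 allows glucocorticoid premedication to be reduced only from the third infusion, depending on how the second went. In a multicentre trial, two sites could run infusion 2 differently while each follows a written instruction.

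**Working it through.** **Inputs.** Stepped rates from Tables 3 and 4 (section 5.2.2); a 1000 mL bag at 1 mg/mL for a 1000 mg dose (section 7.2.1), so 1 mL carries 1 mg; starting rates from sections 5.2.2 and 7.2.4.

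**Formula.** Volume given in the half-hour steps = 0.5 × (sum of the step rates). Duration = time in those steps + (1000 − volume given) / 400.

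**The plan's own durations.**

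- Table 3: 0.5 × (12 + 25 + 50 + 100 + 200 + 300) = 343.5 mL in 3 h; the remaining 656.5 mL at 400 mL/h takes 1.64 h; total 4.64 h. The plan says: "If this schedule is followed, the infusion duration will be approximately 4.6 hours".
- Table 4: 0.5 × (25 + 50 + 100 + 200) = 187.5 mL in 2 h; the remaining 812.5 mL at 400 mL/h takes 2.03 h; total 4.03 h. The plan says: "Duration of the infusion will be approximately 4 hours if this schedule is followed".

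Both tables agree with their own text. The discrepancy lies between 7.2.4 and 5.2.2, not inside the tables.

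**Ratio of starting rates.** 25 / 12 = 2.08, or 25 against 12 mg/h at 1 mg/mL.

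**Drug delivered at infusion 2.** Section 7.2.4 sets only the initial rate, so what follows depends on which table staff then use. Three courses are possible:

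- A: Table 3 throughout, as in 5.2.2.
- B: start at 25 mL/h, then follow Table 3 from its second step.
- C: start at 25 mL/h and run all of Table 4.

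| Time | A (mg) | B (mg) | C (mg) |
|---|---|---|---|
| 0.5 h | 6 | 12.5 | 12.5 |
| 1 h | 18.5 | 25 | 37.5 |
| 2 h | 93.5 | 100 | 187.5 |
| 3 h | 343.5 | 350 | 587.5 |
| Full duration | 4.64 h | 4.63 h | 4.03 h |

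For B, the first half-hour adds 0.5 × (25 − 12) = 6.5 mg and the gap then stays constant; duration = 3 + (1000 − 350)/400 = 4.625 h. For C, the gap at 2 h is 187.5 − 93.5 = 94 mg, and at 3 h it is 587.5 − 343.5 = 244 mg.

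**The case against.** The best defence is that section 5.2.2 plainly governs. Section 7.2.1 says ofatumumab is infused as 5.2.2 specifies. The bullet after the pump setting in 7.2.4 points to 5.2.2. The nursing considerations page sends staff to 5.2.2 and Tables 2 to 4 for rates, and to 7.2.4 only for set-up. A consistent reading also exists. Section 5.2.2 uses the word first for both the 300 mg and the initial 1000 mg infusion; Tables 2 and 3 are both captioned as the 1st infusion, and Table 4 as the subsequent one. In that vocabulary, the two classes in 7.2.4 match the three in 5.2.2.

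This stands as a reason to think error less likely. It does not remove the conflict: 7.2.4 never says that first means first at each strength, and it states a number to be set on the pump immediately before it refers the reader elsewhere.

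A reader might infer more than the documents support:

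- That drug delivery is doubled through the first 2 hours. This holds only under course C, and the 7.2.4 bullet never mentions Table 4.
- That infusion-reaction results are compromised. No infusion-reaction-rate endpoint is specified; section 14.2 plans only the number and percent of patients with toxicities.
- That patients have been harmed. The documents record no such event. Premedication, slowing or interruption for reactions, and close monitoring apply at either rate.

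**Conclusion.** The concern holds as a conflict of wording in a drug-delivery instruction that is still in use. On a literal reading, infusion 2 has two stated starting rates, 2.08 times apart, whenever infusion 1 caused no grade 3 or higher infusion-associated event. The extra drug delivered by 2 h lies between 6.5 mg (course B) and 94 mg (course C) of a 1000 mg dose; the upper figure assumes that staff run the whole of Table 4.

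The reach is limited. It concerns one infusion per patient. Enrollment closed at 27 (section 14.1), and a correction can help only those who have not yet had infusion 2, a number the documents do not give. The overall response rate, type I error and power are unaffected. Nothing here bears on which starting rate is right.

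**What to change.** Reconcile the pump-setting bullet in section 7.2.4 with section 5.2.2 so that the protocol states one starting rate for the first 1000 mg infusion. Define first and subsequent infusion once, and use the terms the same way in both sections and in the captions of Tables 2 to 4. The sponsor decides which rate stands; the edit should follow that decision, whichever section then has to change. Notify pharmacy and nursing staff at all sites.

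The cost is a short wording change in an amendment, with the IRB approval that section 13.1 requires, and a notice to sites. No new procedure, visit or analysis is needed.
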